Appendix 3.3.6 Abnormal Vital Sign Values

Not every vital sign abnormality qualifies as an AE. A vital sign result must be reported as an AE if it meets any of the following criteria:

- Is accompanied by clinical symptoms
- Results in a change in study treatment (e.g., dosage modification, treatment interruption, or treatment discontinuation)
- Results in a medical intervention or a change in concomitant therapy
- Is clinically significant in the physician's judgment

It is the physician's responsibility to review all vital sign findings. Medical and scientific judgment should be exercised in deciding whether an isolated vital sign abnormality should be classified as an AE.

If a clinically significant vital sign abnormality is a sign of a disease or syndrome (e.g., high blood pressure), only the diagnosis (i.e., hypertension) should be recorded in the AE section of the CRF.

Observations of the same clinically significant vital sign abnormality from visit to visit should only be recorded once in the AE section of the CRF (see Appendix 3.3.4 for details on recording persistent AEs).

Appendix 3.3.7 Abnormal Liver Function Tests

The finding of an elevated ALT or AST ($> 3 \times$ the ULN) in combination with either an elevated total bilirubin ($> 2 \times$ the ULN) or clinical jaundice in the absence of cholestasis or other causes of hyperbilirubinemia is considered to be an indicator of severe liver injury. Therefore, physicians must report as an AE the occurrence of either of the following:

- Treatment-emergent ALT or AST $> 3 \times$ ULN in combination with total bilirubin $> 2 \times$ the ULN
- Treatment-emergent ALT or AST $> 3 \times$ ULN in combination with clinical jaundice

The most appropriate diagnosis or (if a diagnosis cannot be established) the abnormal laboratory values should be recorded in the AE section of the CRF (see Appendix 3.3.5) and reported to the marketing authorization holder immediately (i.e., no more than 24 hours after learning of the event) either as an SAE or a non-serious AE of special interest (see Section 10.1.3.1).

Appendix 3.3.8 Deaths

All deaths that occur during the protocol-specified AE reporting period (see Section 10.1.2.1), regardless of relationship to study medicine, must be recorded in the AE section of the eCRF and immediately reported to the marketing authorization holder (see Section 10.1.3.1).

Death should be considered an outcome and not a distinct event. The event or condition that caused or contributed to the fatal outcome should be recorded as the single medical concept on the AE section of the CRF. Generally, only one such event should be reported. The term “**sudden death**” should only be used for the occurrence of an abrupt and unexpected death due to presumed cardiac causes in a patient with or without preexisting heart disease, within 1 hour after the onset of acute symptoms or, in the case of an unwitnessed death, within 24 hours after the patient was last seen alive and stable. If the cause of death is unknown and cannot be ascertained at the time of reporting, “**unexplained death**” should be recorded on the AE section of the CRF. If the cause of death later becomes available (e.g., after autopsy), “unexplained death” should be replaced by the established cause of death.

Appendix 3.3.9 Preexisting Medical Conditions

A preexisting medical condition is one that is present at the screening visit for this study. Such conditions should be recorded on the General Medical History and Baseline Conditions in the CRF.

A preexisting medical condition should be recorded as an AE only if the frequency, severity, or character of the condition worsens during the study. When recording such events in the AE section of the CRF, it is important to convey the concept that the preexisting condition has changed by including applicable descriptors (e.g., “more frequent headaches”).

Appendix 3.3.10 Lack of Therapeutic Efficacy

Events that are clearly consistent with the expected pattern of progression of the underlying disease should not be recorded as AEs. These data will be captured as effectiveness assessment data only. In most cases, the expected pattern of progression will be based on clinical criteria. In rare cases, the determination of clinical progression will be based on symptomatic deterioration. However, every effort should be made to document progression through use of objective criteria. If there is any uncertainty as to whether an event is due to disease progression, it should be reported as an AE. This exception from reporting includes events of disease progression with a fatal outcome which are clearly attributable to disease progression.

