7.2 OBJECTIVES

The primary objective for this study is as follows:

- to estimate OS according to cohorts with cerebral and without cerebral metastases (investigator assessed)

The secondary objectives for this study are as follows:

- to estimate intermediate endpoints, including:
 - PFS (investigator assessed)
 - ORR (CR + PR) (investigator assessed)
 - Intracranial ORR (iORR)
 - Extracranial ORR (eORR)
 - Time to CNS relapse in cohort with cerebral metastases / development of cerebral metastases in cohort with solely extracerebral metastases (investigator

assessed)

- to describe clinical characteristics of patients overall, and according to both cohorts (i.e. demographic data, medical history, information on primary mM, ECOG performance status, serum LDH at baseline, number of extracranial metastatic sites at baseline; in case of brain metastasis: number of brain metastases, largest diameter, symptomatic/asymptomatic brain metastasis, leptomeningeal disease, concomitant therapy for brain metastasis)
- to describe utilization of cobimetinib / vemurafenib (type and number of previous adjuvant and palliative treatments, dosing schedules, treatment beyond progression, reason for discontinuation, subsequent therapies and concomitant medication)
- to describe utilization of cobimetinib / vemurafenib and treatment for brain metastasis (prior local treatment for brain metastases, concomitant radiotherapy or surgery, type of radiotherapy, steroid use prophylactic or therapeutic, use of anticonvulsiva)
- to describe patient reported outcome using the EORTC QLQ-C30 questionnaire

Safety Objectives

The safety objectives for this study are as follows:

The incidence of all adverse events (AEs) and serious adverse events (SAEs) in cobimetinib / vemurafenib treated patients.

- All protocol-specified adverse events (AEs) described in this section will be reported and graded according to the National Cancer Institute Common Terminology Criteria for Adverse Events version 4 (CTCAE v4.03).
- Incidence and outcomes of serious and non-serious AEs of interest (i.e., those AEs identified by Genentech/Roche as potential or known risks of cobimetinib and/or vemurafenib use)
- These AEs of interest for the combination of vemurafenib and cobimetinib include the following:
 - Any grade serous retinopathy
 - Any grade retinal vein occlusion
 - Grade \geq 2 left ventricular dysfunction

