- Rhabdomyolysis grade ≥ 3 CPK elevation (including elevations of CPK-MM in conjunction with other laboratory evidence (aldolase and urine myoglobin), clinical features consistent with rhabdomyolysis such as muscle pain, sings or renal failure, or dark red or brown urine)
- Grade ≥ 3 hemorrhage event or any grade cerebral hemorrhage
- Grade ≥ 3 rash
- Grade ≥ 3 photosensitivity
- Events suggestive of drug induced liver injury or other Grade ≥ 3 hepatotoxicity as defined by:
 - o Grade ≥ 3 elevations of aspartate aminotransferase (AST), alanine aminotransferase (ALT), serum bilirubin, gamma-glutamyl transpeptidase/transferase (GGT), OR cases of elevated ALT or AST in combination with either an elevated bilirubin or clinical jaundice
- AE potentially associated with prolongation of cardiac repolarization
- New or progression of RAS mutant malignancy, cutaneous squamous cell carcinoma, new primary melanoma, or basal cell carcinoma, or other new malignancies.

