10.1.1.1 Adverse Events

According to the International Conference of Harmonisation (ICH), an AE is any untoward medical occurrence in a patient or clinical investigation subject administered a pharmaceutical product, regardless of causal attribution. An AE can therefore be any of the following:

- Any unfavorable and unintended sign (including an abnormal laboratory finding), symptom, or disease temporally associated with the use of a medicinal product, whether or not considered related to the medicinal product
- Any new disease or exacerbation of an existing disease (a worsening in the character, frequency, or severity of a known condition), except as described in Appendix 3
- Recurrence of an intermittent medical condition (e.g., headache) not present at baseline
- Any deterioration in a laboratory value or other clinical test (e.g., electrocardiogram [ECG], X-ray) that is associated with symptoms or leads to a change in study treatment or concomitant treatment or discontinuation from study medicine.

10.1.1.2 Assessment of Serious Adverse Events (Immediately Reportable to the Marketing Authorization Holder), Non-serious Adverse Events of Special Interest (AESI) and Other Non-serious Adverse Events

Serious Adverse Events

An SAE is any AE that meets any of the following criteria:

- Is fatal (i.e., the AE actually causes or leads to death)
- Is life-threatening (NOTE: The term “life-threatening” refers to an event in which the patient was at immediate risk of death at the time of the event; it does not refer to an event that hypothetically might have caused death if it were more severe.)
- Requires or prolongs inpatient hospitalization (see A)
- Results in persistent or significant disability/incapacity (i.e., the AE results in substantial disruption of the patient’s ability to conduct normal life functions)
- Is a congenital anomaly/birth defect in a neonate/infant born to a mother exposed to study medicine
- Is a significant medical event in the physician’s judgment (e.g., may jeopardize the patient or may require medical/surgical intervention to prevent one of the outcomes listed above)

The terms “severe” and “serious” are not synonymous. Severity refers to the intensity of an AE (e.g., rated as mild, moderate, or severe, or according to NCI CTCAE criteria; see Appendix 3); the event itself may be of relatively minor medical significance (such as severe headache without any further findings).

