Appendix 3.3.11 Hospitalization or Prolonged Hospitalization

Any AE that results in hospitalization or prolonged hospitalization should be documented and reported as an SAE (per the definition of SAE in Section 10.1.1.2), except as outlined below.

The following hospitalization scenarios are not considered to be SAEs:

- Hospitalization for respite care
- Hospitalization for a preexisting condition, provided that all of the following criteria are met:
 - The hospitalization was planned prior to the study or was scheduled during the study when elective surgery became necessary because of the expected normal progression of the disease.
 - The patient has not suffered an AE.

Hospitalization due solely to progression of the underlying cancer. The following hospitalization scenarios are not considered to be SAEs but should be reported as AEs instead:

- Hospitalization that was necessary because of patient requirement for outpatient care outside of normal outpatient clinic operating hours

Appendix 3.3.12 Overdoses, Misuses, Abuses, Off-Label Use, Occupational Exposure, or Medication Error

Any overdose, misuse, abuse, off-label use, occupational exposure, medication error (including intercepted or potential), or any other incorrect administration of medicine under observation should be noted in the Drug Administration section of the CRF. Any overdose, misuse, abuse, off-label use, occupational exposure or medication error (including intercepted or potential) reports must be forwarded to the marketing authorization holder with or without an AE.

Reports with or without an AE should be forwarded to the marketing authorization holder as per non-serious timelines. If the associated AE fulfills the seriousness criteria, the event should be reported to the marketing authorization holder immediately (i.e., no more than 24 hours after learning of the event, see Section 10.1.3.1).

For the purpose of reporting cases of suspected adverse reactions, an occupational exposure to a medicine means an exposure to a medicine as a result of one's professional or non-professional occupation.

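### The progression exemption in Appendix 3.3.10 has no exception for AEs of interest, so a non-fatal bleed in a known brain metastasis can go unrecorded although any-grade cerebral hemorrhage is a stated safety objective

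*Protocol*

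**What the plan says.** The safety objectives in protocol Section 7.2, repeated in the synopsis, include "Incidence and outcomes of serious and non-serious AEs of interest". The list that follows contains "Grade ≥ 3 hemorrhage event or any grade cerebral hemorrhage". Bleeding inside a known lesion is not excluded.

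Appendix 3.3.10 gives a general rule for disease progression: "Events that are clearly consistent with the expected pattern of progression of the underlying disease should not be recorded as AEs". It then says where such events go: "These data will be captured as effectiveness assessment data only". A safeguard follows: "If there is any uncertainty as to whether an event is due to disease progression, it should be reported as an AE". AEs of interest are not mentioned.

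The AE definition in Section 10.1.1.1 gives way to the appendix. Worsening in the "severity of a known condition), except as described in Appendix 3" counts as an AE. Appendix 3.3.11, as the text reads, closes its list of admissions that are not SAEs with "Hospitalization due solely to progression of the underlying cancer".

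**The concern.** The objective asks for a count of all cerebral hemorrhages, whatever their cause. The recording rule lets the site settle the cause first and, if it is confident of progression, record nothing in the AE section. These are different quantities, and the protocol does not say which instruction prevails.

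The difference matters most in Cohort B. Every patient there has a cerebral lesion to which a bleed could be attributed, and Section 6.2 says the pivotal study did not include patients with brain metastases. Whether a bleed is due to the drug or to the lesion is what the causality assessment in Appendix 3.2 is for. Under Appendix 3.3.10 that question can be answered before any record exists, so two sites could handle the same bleed differently and both comply.

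**Working it through.** **Step 1: does any other section bring the event back?**

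- *AE definition (Section 10.1.1.1).* It covers worsening of a known condition but defers to Appendix 3, so it does not override the exemption.
- *AESI list (Section 10.1.1.2).* Cerebral hemorrhage is not on it, so the 24-hour AESI route does not restore the event. The duty there to collect all other non-serious AEs applies only to what still counts as an AE.
- *Hospitalization (Appendix 3.3.11).* An admission judged to be due only to progression is not an SAE, so admission need not bring the event back.
- *Safeguard (Appendix 3.3.10).* It catches every case in which the site has doubt. It does not reach a site that has none.
- *Deaths (Section 10.1.2.2 and Appendix 3.3.8).* All deaths in the reporting period go into the AE section, whereas the last sentence of Appendix 3.3.10 exempts fatal events clearly due to progression. That is a separate conflict. The gap discussed here concerns non-fatal bleeds.

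**Step 2: could an omitted bleed be found in the effectiveness data?** The relevant items in Section 8.4.2 and Appendix 2 are tumor response, date of progression, local treatment for brain metastasis, and date and reason of death. None is a hemorrhage field. A bleed handled as progression would appear at most as PD.

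**Step 3: size per missed event.**

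- Planned Cohort B (Section 8.5): 225 × 0.30 = 67.5, which matches the stated 68.
- One missed event in Cohort B: 1/68 = 1.5 percentage points.
- One missed event in all patients, if all 225 are treated: 1/225 = 0.44 percentage points.

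**Step 4: illustration only.** The protocol gives neither a hemorrhage rate nor a share handled as progression. Both are assumed below. Intervals are exact (Clopper-Pearson) 95% limits with denominator 68.

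| True events | True incidence (95% CI) | Recorded events | Reported incidence (95% CI) |
|---|---|---|---|
| 3 | 4.4% (0.9–12.4) | 2 | 2.9% (0.4–10.2) |
| 7 | 10.3% (4.2–20.1) | 4 | 5.9% (1.6–14.4) |
| 14 | 20.6% (11.7–32.1) | 7 | 10.3% (4.2–20.1) |

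In the second row 3 events are missed: 3/68 = 4.4 points in Cohort B and 3/225 = 1.3 points overall. In the third row 7 are missed: 7/68 = 10.3 points and 7/225 = 3.1 points. In every row the intervals for true and reported incidence overlap widely.

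**The case against.** The best defence is that the exemption is narrow. It needs a clear match with an expected pattern, and any doubt leads to reporting. Nowhere does the protocol call bleeding into a metastasis expected progression. Section 7.2 presents its list as potential or known risks of the drugs, so a site has a named drug explanation in front of it and certainty is hard to justify. Appendix 3.3.9 also makes a preexisting condition an AE when its character worsens, and Appendix 3.3.3 keeps severe or serious secondary events separate. On that reading the specific listing governs, and a careful site records the bleed.

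Much of this stands. It makes omission less likely and rules out saying that the protocol forbids recording these bleeds. It does not close the gap, because the protocol does not state that the listing prevails and leaves the decision to each site. The CRF completion manual mentioned in Section 8.6.2 might settle it, but it is not part of the protocol.

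A reader might extend the point to liver test elevations in patients with liver metastases. The document largely covers these. Appendix 3.3.7 requires reporting of combined transaminase and bilirubin elevations or jaundice, Appendix 3.3.5 requires it for values that change treatment, need intervention or are clinically significant, and Section 10.1.1.2 lists Grade 4 elevations. At most, isolated Grade 3 values meeting none of these criteria remain.

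A reader might also infer that safety comparisons between sites or cohorts would be invalid. None is planned. Section 8.7 is descriptive without hypothesis testing, Section 8.7.1 takes all treated patients together, and the separate analysis by cohort in Section 8.7.2 concerns efficacy.

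**Conclusion.** The point holds as an unreconciled recording rule. Undercounting of non-fatal cerebral hemorrhage is possible, mainly in Cohort B. Any error from this source is downward, since the rule can only remove events. The size is 1.5 percentage points per missed event if incidence is reported for Cohort B, and about 0.4 points in the overall safety population, assuming 68 and 225 treated patients.

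It would go too far to say that the incidence will be biased, or by how much. That needs a bleeding rate and an omission share, and the protocol supplies neither. No stated figure in the protocol is wrong. This is a cheap improvement that protects a named safety outcome, not a flaw that undermines the study.

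**What to change.** Reconcile the two sections by adding one sentence to Appendix 3.3.10, with a pointer in Appendix 3.3.11. Suggested wording: *The progression exemption does not apply to the AEs of interest in Section 7.2 or the AESIs in Section 10.1.1.2; any cerebral hemorrhage, including one in a known metastasis, is recorded as an AE with a causality assessment, whatever its attribution to progression.*

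An eCRF flag for location in a known metastasis is optional. It would allow the incidence to be shown in total and split by location.

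The cost is one sentence, one cross-reference and slightly more AE reports. Only recording changes. No assessment or treatment is added, so the study remains non-interventional.

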8.3.3 Primary Safety Variables

The primary safety variables for this study are as follows:

- Total adverse events
- Serious adverse events
- \geq grade 3 adverse events
- Adverse events leading to treatment discontinuation
- Adverse events of special interest

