10.1.2.2 Procedures for Recording Adverse Events

Physicians should use correct medical terminology/concepts when recording AEs in the AE section of the CRF. Colloquialisms and abbreviations should be avoided.

Only one AE term should be recorded in the event field of the CRF.

See Appendix 3 for further specific instruction regarding:

- Diagnosis versus signs and symptoms
- Adverse Events occurring secondary to other Adverse Events
- Persistent or recurrent Adverse Events
- Abnormal Laboratory Values
- Abnormal Vital Sign Values
- Abnormal Liver Function Tests
- Deaths
 - All events with an outcome or consequence of death should be classified as serious adverse events (SAEs) and reported to the marketing authorization holder immediately. All deaths that occur during the protocol-specified AE reporting period, regardless of relationship to study medicine, must be recorded in the AE section of the CRF and immediately reported to the marketing authorization holder
- Pre-existing Medical Conditions
- Lack of Therapeutic Efficacy or worsening of Malignant Melanoma
- Hospitalization or Prolonged Hospitalization
- Overdoses, Misuses, Abuses, Off-Label Use, Occupational Exposure, or Medication Error
- Drug Interactions
- Quality Defects and Falsified Medicinal Products

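### Deaths from melanoma progression are both required in and exempt from the AE section, so SAE incidence has no single definition

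*Protocol*

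**What the plan says.** Two instructions apply to a patient who dies of melanoma during the AE reporting period.

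**Record it.** Section 10.1.2.2 gives fatal events SAE status ("All events with an outcome or consequence of death should be classified as serious adverse events (SAEs"). It adds that all deaths in the period, "regardless of relationship to study medicine, must be recorded in the AE section of the CRF and immediately reported", go to the marketing authorization holder. Appendix 3.3.8 repeats the duty ("must be recorded in the AE section of the eCRF and immediately reported to the marketing authorization holder") and says what to enter: "The event or condition that caused or contributed to the fatal outcome should be recorded as the single medical concept". For a melanoma death that concept would be the progression itself. Neither place makes an exception for progression.

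**Do not record it.** Appendix 3.3.10 states: "Events that are clearly consistent with the expected pattern of progression of the underlying disease should not be recorded as AEs". Such data are to be kept as effectiveness data only, and fatal cases are expressly covered: "This exception from reporting includes events of disease progression with a fatal outcome which are clearly attributable to disease progression". Events whose link to progression is uncertain are still to be reported as AEs.

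Section 8.3.3 lists "Serious adverse events" and grade 3 or higher AEs among the primary safety variables. Section 8.7.1 plans summaries of AEs leading to death and of SAEs including deaths. Section 10.1.2.1 runs AE collection from enrolment to the end of the patient's observation period. Separately from the AE section, Appendix 2 collects the date of death and whether it was due to melanoma (yes, no or unknown).

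**The concern.** A death clearly due to melanoma falls under both instructions, and a site cannot follow both. In a population with advanced melanoma such deaths may be a large part of all deaths, so this is not a marginal case. If sites resolve the conflict differently, reported SAE incidence, grade 3 or higher incidence (through grade 5) and the count of fatal AEs become a mixture of treatment safety and melanoma mortality whose proportions depend on local reading. Because SAEs must reach the marketing authorization holder within 24 hours (Section 10.1.3.1), sites are also left unsure of a reporting duty. Overall survival is not at stake, since the date of death is collected independently.

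**Working it through.** **1. Does the text rank the two rules?** The AE definition in Section 10.1.1.1 yields to Appendix 3, but both Appendix 3.3.8 (record) and Appendix 3.3.10 (exempt) lie in Appendix 3, so that clause does not decide between them. Section 10.1.2.2 points to Appendix 3 both for deaths and for worsening of melanoma, yet spells out only the death rule, without an exception. Appendices 3.3.8 and 3.3.10 do not mention each other. The instruction to report when uncertain does not help, because the conflict concerns deaths that are clearly progression.

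**2. Inputs (Sections 8.5 and 8.1).** Cohort A: 157 patients, assumed median OS 25 months. Cohort B: 68 patients, assumed median 12 months. Recruitment 18 months, follow-up up to 18 months, 3 years in all. The protocol states no expected SAE incidence.

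**3. Anchor: the protocol's own confidence intervals.** Assume exponential survival, with d = N × (1 − 2^(−t/m)) deaths and interval m ± 1.96 × m/√d, at t = 18 months.
- B: d = 68 × (1 − 2^(−18/12)) = 44.0; 12 ± 1.96 × 12/√44.0 = [8.45; 15.55], against the stated [8.5; 15.5].
- A: d = 157 × (1 − 2^(−18/25)) = 61.7; 25 ± 1.96 × 25/√61.7 = [18.8; 31.2], against the stated [19; 31].

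The exponential model reproduces both intervals closely, so it is a fair basis for the number of deaths the plan implies.

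**4. Deaths in the AE window.** The window per patient is not pinned down, so two versions are shown. For uniform accrual over 18 months plus 18 months of follow-up, P(death) = 1 − [S(18) − S(36)]/(18λ), with λ = ln 2/m.

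| Window per patient | Cohort A | Cohort B | Total of 225 |
|---|---|---|---|
| 18 months | 61.7 (39%) | 44.0 (65%) | 105.6 (47%) |
| 18 to 36 months | 82.0 (52%) | 53.1 (78%) | 135.0 (60%) |

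With 10% dropout by 18 months, the second row falls to 126.5 (56%). If only 12 months per patient counted, there would be about 78 deaths (35%).

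**5. Shift in SAE incidence between the rules.** A patient changes status only if he or she dies in the window, the death is clearly progression, and there is no other SAE:

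shift = P(death) × share clearly progression × (1 − share of those patients with another SAE)

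- Ceiling (shares 100% and 0%): 47 to 60 points.
- The two shares are not in the protocol. Assuming 70-90% and 30-50%:
  - 18 months: 0.47 × 0.70 × 0.50 = 16.4 to 0.47 × 0.90 × 0.70 = 29.6 points.
  - 18 to 36 months: 0.60 × 0.70 × 0.50 = 21.0 to 0.60 × 0.90 × 0.70 = 37.8 points.
- Assuming 50% and 90%: 0.47 × 0.50 × 0.10 = 2.3 and 0.60 × 0.50 × 0.10 = 3.0 points.

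**The case against.** The strongest reply is that this is a general rule with an exception. Appendix 3.3.10 calls itself an exception and names fatal outcomes, which makes it the more specific text. An SAE is defined as a kind of AE, so an event that is not an AE cannot be one. Appendix 3.3.8 treats death as an outcome, not an event. Appendix 3.3.11 also exempts hospitalization due solely to progression. This reading is plausible, but the protocol never states it, and Section 10.1.2.2 and Appendix 3.3.8 are worded without exception. The contradiction stands.

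Other parts of the defence do limit the point. Three stronger conclusions that a reader might draw are not supported:

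- That the roughly 40 sites will in fact apply different rules. The protocol provides CRF training and a manual, data queries, source data verification and a data review meeting. None is shown to settle this question, but divergence is a risk, not a fact.
- That the gap between SAE incidence with all deaths counted and the contribution of non-melanoma deaths alone is the size of the shift. Those are unlike quantities: patients with another SAE count under both rules.
- That Cohort B will be presented as less safe. Section 8.7.1 states no safety analysis by cohort; only efficacy is stated to be analysed separately.

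The reason-for-death field also allows partial recovery at analysis. It is only partial: the field has an unknown category, a death due to melanoma need not be one clearly attributable to progression, and the field cannot make AE-section entries or immediate reports uniform afterwards.

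**Conclusion.** The point holds as an internal contradiction: followed as written, the protocol does not yield one SAE count for deaths clearly due to progression. It bears on SAE incidence, grade 3 or higher AEs and AEs leading to death, and not on overall survival. The ceiling of 47 to 60 points rests on the protocol's medians, exponential survival and an AE window of 18 months or 18 to 36 months per patient. Below that ceiling the size depends on assumptions: tens of points are possible under the mid-range shares, but the effect is minor if nearly all patients who die of progression have another SAE anyway. The protocol cannot say which applies.

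**What to change.** Reconcile Section 10.1.2.2, Appendix 3.3.8 and Appendix 3.3.10 into one rule of the sponsor's choosing, worded identically in all three places or linked by explicit cross-reference. Which rule to adopt is for the sponsor. In Section 8.7.1, state that SAE, grade 3 or higher and fatal AE incidence will be presented both including and excluding deaths due to melanoma, using the reason for death already collected under Appendix 2. The cost is small wording edits, a note to sites and one extra row in the affected tables; no new data are needed.
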